5.8 Rescue Medications & Supportive Care

5.8.1 Supportive Care Guidelines

Subjects should receive appropriate supportive care measures as deemed necessary by the treating investigator. Suggested supportive care measures for the management of adverse events with potential immunologic etiology are outlined below. Where appropriate, these guidelines include the use of oral or intravenous treatment with corticosteroids as well as additional anti-inflammatory agents if symptoms do not improve with administration of corticosteroids. Note that several courses of steroid tapering may be necessary as symptoms may worsen when the steroid dose is decreased. For each disorder, attempts should be made to rule out other causes such as metastatic disease or bacterial or viral infection, which might require additional supportive care. The treatment guidelines are intended to be applied when the investigator determines the events to be related to pembrolizumab.

Note: if after the evaluation the event is determined not to be related, the investigator does not need to follow the treatment guidance (as outlined below). Refer to Section 5.2.1 for dose modification.

It may be necessary to perform conditional procedures such as bronchoscopy, endoscopy, or skin photography as part of evaluation of the event.

- **Pneumonitis:**
 - For **Grade 2 events**, treat with systemic corticosteroids. When symptoms improve to Grade 1 or less, steroid taper should be started and continued over no less than 4 weeks.
 - For **Grade 3-4 events**, immediately treat with intravenous steroids. Administer additional anti-inflammatory measures, as needed.
 - Add prophylactic antibiotics for opportunistic infections in the case of prolonged steroid administration.
- **Diarrhea/Colitis:**

Subjects should be carefully monitored for signs and symptoms of enterocolitis (such as diarrhea, abdominal pain, blood or mucus in stool, with or without fever) and of bowel perforation (such as peritoneal signs and ileus).

 - All subjects who experience diarrhea/colitis should be advised to drink liberal quantities of clear fluids. If sufficient oral fluid intake is not feasible, fluid and electrolytes should be substituted via IV infusion. For Grade 2 or higher diarrhea, consider GI consultation and endoscopy to confirm or rule out colitis.
 - For **Grade 2 diarrhea/colitis**, administer oral corticosteroids.
 - For **Grade 3 or 4 diarrhea/colitis**, treat with intravenous steroids followed by high dose oral steroids.
 - When symptoms improve to Grade 1 or less, steroid taper should be started and continued over no less than 4 weeks.
- **Type 1 diabetes mellitus (if new onset, including diabetic ketoacidosis [DKA]) or \geq Grade 3 Hyperglycemia, if associated with ketosis (ketonuria) or metabolic acidosis (DKA)**
 - For **T1DM or Grade 3-4 Hyperglycemia**

- Insulin replacement therapy is recommended for Type I diabetes mellitus and for Grade 3-4 hyperglycemia associated with metabolic acidosis or ketonuria.
- Evaluate patients with serum glucose and a metabolic panel, urine ketones, glycosylated hemoglobin, and C-peptide.
- **Hypophysitis:**
 - For **Grade 2** events, treat with corticosteroids. When symptoms improve to Grade 1 or less, steroid taper should be started and continued over no less than 4 weeks. Replacement of appropriate hormones may be required as the steroid dose is tapered.
 - For **Grade 3-4** events, treat with an initial dose of IV corticosteroids followed by oral corticosteroids. When symptoms improve to Grade 1 or less, steroid taper should be started and continued over no less than 4 weeks. Replacement of appropriate hormones may be required as the steroid dose is tapered.
- **Hyperthyroidism or Hypothyroidism:**

Thyroid disorders can occur at any time during treatment. Monitor patients for changes in thyroid function (at the start of treatment, periodically during treatment, and as indicated based on clinical evaluation) and for clinical signs and symptoms of thyroid disorders.

 - **Grade 2** hyperthyroidism events (and **Grade 2-4** hypothyroidism):
 - In hyperthyroidism, non-selective beta-blockers (e.g. propranolol) are suggested as initial therapy.
 - In hypothyroidism, thyroid hormone replacement therapy, with levothyroxine or liothyronine, is indicated per standard of care.
 - **Grade 3-4** hyperthyroidism
 - Treat with an initial dose of IV corticosteroid followed by oral corticosteroids. When symptoms improve to Grade 1 or less, steroid taper should be started and continued over no less than 4 weeks. Replacement of appropriate hormones may be required as the steroid dose is tapered.
- **Hepatic:**
 - For **Grade 2** events, monitor liver function tests more frequently until returned to baseline values (consider weekly).
 - Treat with IV or oral corticosteroids
 - For **Grade 3-4** events, treat with intravenous corticosteroids for 24 to 48 hours.
 - When symptoms improve to Grade 1 or less, a steroid taper should be started and continued over no less than 4 weeks.
- **Renal Failure or Nephritis:**
 - For **Grade 2** events, treat with corticosteroids.
 - For **Grade 3-4** events, treat with systemic corticosteroids.
 - When symptoms improve to Grade 1 or less, steroid taper should be started and continued over no less than 4 weeks.

- **Management of Infusion Reactions:** Signs and symptoms usually develop during or shortly after drug infusion and generally resolve completely within 24 hours of completion of infusion.

Table 2 below shows treatment guidelines for subjects who experience an infusion reaction associated with administration of pembrolizumab (MK-3475).

Table 5 Infusion Reaction Treatment Guidelines

NCI CTCAE Grade	Treatment	Premedication at subsequent dosing

Grade 1 Mild reaction; infusion interruption not indicated; intervention not indicated
	
Increase monitoring of vital signs as medically indicated until the subject is deemed medically stable in the opinion of the investigator.
	
None

Grade 2 Requires infusion interruption but responds promptly to symptomatic treatment (e.g., antihistamines, NSAIDS, narcotics, IV fluids); prophylactic medications indicated for <=24 hrs
	
Stop Infusion and monitor symptoms. Additional appropriate medical therapy may include but is not limited to: IV fluids Antihistamines NSAIDS Acetaminophen Narcotics
 
Increase monitoring of vital signs as medically indicated until the subject is deemed medically stable in the opinion of the investigator. If symptoms resolve within one hour of stopping drug infusion, the infusion may be restarted at 50% of the original infusion rate (e.g., from 100 mL/hr to 50 mL/hr). Otherwise dosing will be held until symptoms resolve and the subject should be premedicated for the next scheduled dose.
 
Subjects who develop Grade 2 toxicity despite adequate premedication should be permanently discontinued from further trial treatment administration.
	
Subject may be premedicated 1.5h (\pm 30 minutes) prior to infusion of pembrolizumab (MK-3475) with:
 
Diphenhydramine 50 mg po (or equivalent dose of antihistamine).
 
Acetaminophen 500-1000 mg po (or equivalent dose of antipyretic).


Grades 3 or 4 Grade 3: Prolonged (i.e., not rapidly responsive to symptomatic medication and/or brief interruption of infusion); recurrence of symptoms following initial improvement; hospitalization indicated for other clinical sequelae (e.g., renal impairment, pulmonary infiltrates)
	
Stop Infusion. Additional appropriate medical therapy may include but is not limited to: IV fluids Antihistamines NSAIDS Acetaminophen Narcotics Oxygen Pressors Corticosteroids Epinephrine
	
No subsequent dosing

NCI CTCAE Grade	Treatment	Premedication at subsequent dosing
Grade 4: Life-threatening; pressor or ventilatory support indicated	Increase monitoring of vital signs as medically indicated until the subject is deemed medically stable in the opinion of the investigator. Hospitalization may be indicated. Subject is permanently discontinued from further trial treatment administration.	
Appropriate resuscitation equipment should be available in the room and a physician readily available during the period of drug administration.		

5.9 Diet/Activity/Other Considerations

5.9.1 Diet

Subjects should maintain a normal diet unless modifications are required to manage an AE such as diarrhea, nausea or vomiting.

5.9.2 Contraception

Pembrolizumab may have adverse effects on a fetus in utero. Furthermore, it is not known if pembrolizumab has transient adverse effects on the composition of sperm. Non-pregnant, non-breast-feeding women may be enrolled if they are willing to use 2 methods of birth control or are considered highly unlikely to conceive. Highly unlikely to conceive is defined as 1) surgically sterilized, or 2) postmenopausal (a woman who is ≥ 45 years of age and has not had menses for greater than 1 year will be considered postmenopausal), or 3) not heterosexually active for the duration of the study. The two birth control methods can be either two barrier methods or a barrier method plus a hormonal method to prevent pregnancy. Subjects should start using birth control from study Visit 1 throughout the study period up to 120 days after the last dose of study therapy.

The following are considered adequate barrier methods of contraception: diaphragm, condom (by the partner), copper intrauterine device, sponge, or spermicide. Appropriate hormonal contraceptives will include any registered and marketed contraceptive agent that contains an estrogen and/or a progestational agent (including oral, subcutaneous, intrauterine, or intramuscular agents).

Subjects should be informed that taking the study medication may involve unknown risks to the fetus (unborn baby) if pregnancy were to occur during the study. In order to participate in the study they must adhere to the contraception requirement (described above) for the duration of the study and during the follow-up period defined in section 7.2.2 – Reporting of Pregnancy and Lactation. If there is any question that a subject will not reliably comply with the requirements for contraception, that subject should not be entered into the study.

5.9.3 Use in Pregnancy

If a subject inadvertently becomes pregnant while on treatment with pembrolizumab, the subject will immediately be removed from the study. The site will contact the subject at least

monthly and document the subject's status until the pregnancy has been completed or terminated. The outcome of the pregnancy will be reported to the PI and to Merck without delay and within 24 hours if the outcome is a serious adverse experience (e.g., death, abortion, congenital anomaly, or other disabling or life-threatening complication to the mother or newborn). The study investigator will make every effort to obtain permission to follow the outcome of the pregnancy and report the condition of the fetus or newborn to the PI and Merck. If a male subject impregnates his female partner the study personnel at the site must be informed immediately and the pregnancy reported to the PI and to Merck and followed as described above and in Section 7.2.2.

5.9.4 Use in Nursing Women

It is unknown whether pembrolizumab is excreted in human milk. Since many drugs are excreted in human milk, and because of the potential for serious adverse reactions in the nursing infant, subjects who are breast-feeding are not eligible for enrolment.

5.10 Subject Withdrawal/Discontinuation Criteria

Subjects may withdraw consent at any time for any reason or be dropped from the trial at the discretion of the investigator should any untoward effect occur. In addition, a subject may be withdrawn by the investigator or the PI if enrollment into the trial is inappropriate, the trial plan is violated, or for administrative and/or other safety reasons. Specific details regarding discontinuation or withdrawal are provided in Section 7.1.3.

A subject must be discontinued from the trial for any of the following reasons:

- The subject or legal representative (such as a parent or legal guardian) withdraws consent.
- Confirmed radiographic disease progression
- Unacceptable adverse experiences
- Intercurrent illness that prevents further administration of treatment
- Investigator's decision to withdraw the subject
- The subject has a confirmed positive serum pregnancy test
- Noncompliance with trial treatment or procedure requirements
- The subject is lost to follow-up
- Administrative reasons

The End of Treatment and Follow-up visit procedures are listed in Section 6 (Trial Flow Chart) and Section 7.1.4 (Visit Requirements). After the end of treatment, each subject will be followed for 30 days for adverse event monitoring. Subjects who discontinue for reasons other than progressive disease will have post-treatment follow-up for disease status until disease progression, initiating a non-study cancer treatment, withdrawing consent or becoming lost to follow-up.

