5.6.2 Pembrolizumab Treatment

Patients randomized to the pembrolizumab arm will be treated with 200 mg pembrolizumab Q3W for 2 cycles or until unacceptable side effects, starting on the first day of radiotherapy.

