Renal Failure or Nephritis	2	Toxicity resolves to Grade 0-1	Toxicity does not resolve within 12 weeks of last dose or inability to reduce corticosteroid to 10 mg or less of prednisone or equivalent per day within 12 weeks
	3-4	Permanently discontinue	Permanently discontinue
All Other Drug-Related Toxicity ^c	3 or Severe	Toxicity resolves to Grade 0-1	Toxicity does not resolve within 12 weeks of last dose or inability to reduce corticosteroid to 10 mg or less of prednisone or equivalent per day within 12 weeks
	4	Permanently discontinue	Permanently discontinue

Note: Permanently discontinue for any severe or Grade 3 drug-related AE that recurs or any life-threatening event.

^a For patients with liver metastasis who begin treatment with Grade 2 AST or ALT, if AST or ALT increases by greater than or equal to 50% relative to baseline and lasts for at least 1 week then patients should be discontinued.

^b If symptoms resolve within one hour of stopping drug infusion, the infusion may be restarted at 50% of the original infusion rate (e.g., from 100 mL/hr to 50 mL/hr). Otherwise dosing will be held until symptoms resolve and the subject should be premedicated for the next scheduled dose; Refer to Table 2 – Infusion Treatment Guidelines for further management details.

^c Patients with intolerable or persistent Grade 2 drug-related AE may hold study medication at physician discretion. Permanently discontinue study drug for persistent Grade 2 adverse reactions for which treatment with study drug has been held, that do not recover to Grade 0-1 within 12 weeks of the last dose.

In case toxicity does not resolve to Grade 0-1 within 12 weeks after last infusion, trial treatment should be discontinued. Subjects with a laboratory adverse event still at Grade 2 after 12 weeks may continue treatment in the trial only if asymptomatic and controlled. For information on the management of adverse events, see Section 5.7.1.

Subjects who experience a recurrence of the same severe or life-threatening event at the same grade or greater with re-challenge of pembrolizumab should be discontinued from trial treatment.

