5.11 Subject Replacement Strategy

Subjects that fail to undergo the trimodality treatment will be replaced.

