7.1.3 Withdrawal/Discontinuation

When a subject discontinues/withdraws prior to trial completion, all applicable activities scheduled for the final trial visit should be performed at the time of discontinuation. Any adverse events which are present at the time of discontinuation/withdrawal should be followed in accordance with the safety requirements outlined in Section 7.2 - Assessing and Recording Adverse Events.

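### Section 5.10 takes patients off the trial, not only off treatment, for undefined toxicity or intercurrent illness, so some timed immune samples are not secured

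*Combined protocol and SAP*

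**What the plan says.** Section 5.10 introduces its list with "A subject must be discontinued from the trial for any of the following reasons". Two entries matter here: "Unacceptable adverse experiences", for which 5.10 gives no grade, and "Intercurrent illness that prevents further administration of treatment".

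Other sections deal with toxicity at the level of the drug. Section 5.6.2 gives "200 mg pembrolizumab Q3W for 2 cycles or until unacceptable side effects". Section 5.6.2.1 says "In case toxicity does not resolve to Grade 0-1 within 12 weeks after last infusion, trial treatment should be discontinued". Table 5 in 5.8.1, for grade 3 or 4 infusion reactions, says "Subject is permanently discontinued from further trial treatment administration".

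Several provisions apply after discontinuation:
- Section 7.1.3 says that "all applicable activities scheduled for the final trial visit should be performed at the time of discontinuation".
- Section 5.10 refers to the end-of-treatment and follow-up procedures in the flow chart. The follow-up column there includes immunophenotyping, which 7.1.2.10 times at one week after surgery and at 6 months.
- Section 5.10 continues disease-status follow-up for patients who stop for reasons other than progression.
- Adverse events are recorded for 90 days after treatment stops under 7.2 (5.10 itself says 30 days).

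Section 5.11 reads "Subjects that fail to undergo the trimodality treatment will be replaced". No analysis population is defined, and nothing says how a replaced patient is analysed.

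**The concern.** The second primary objective (3.1) is the immune response in tumour, nodes and blood. Sections 8.2.1 to 8.2.3 compare it within patients and between arms, with 10 patients per arm. Those comparisons need samples at fixed times after treatment starts. A rule that ends trial participation because of toxicity or illness takes out patients according to something that happened after randomisation. This may occur more often in the combination arm, although the rule covers both arms and the protocol gives no rates. A sample not taken on schedule cannot be recovered at analysis.

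An investigator also faces two instructions for the same event: stop pembrolizumab, or discontinue the patient from the trial. The second is the one that puts data at risk. The illness entry shows the difficulty most clearly, because being unable to give more treatment is itself made a reason to leave the trial.

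**Working it through.** The protocol states no removal rate, alpha, power or standard deviation (5.2 declines a formal power calculation). There is therefore no planned figure to reproduce. Rates and effect sizes below are assumptions and are marked as such.

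**1. What falls due after an early removal.** Inputs: fractions every second day (Table 2), starting on day 1 and ignoring weekends; EBUS between weeks 2 and 3 after SBRT (5.5.1); CT within two weeks before resection (5.4); five blood samples (7.1.2.10).
- SBRT ends on day 5 (3 fractions) or day 9 (5 fractions).
- Second EBUS: 5 + 14 = 19 to 5 + 21 = 26, or 9 + 14 = 23 to 9 + 21 = 30.
- Surgery by the flow chart: day 56 to 70, so the CT window opens at 56 − 14 = day 42 at the earliest.
- Surgery by 5.6.3, counting 8 to 10 weeks from the end of SBRT: 5 + 56 = day 61 to 9 + 70 = day 79, so the CT window opens at 61 − 14 = day 47 at the earliest. The two sections do not agree, and the exact days depend on which is used.

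**2. What is secured.** Take removal after the baseline sample and before day 21.

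| Item outstanding | Provision after discontinuation |
|---|---|
| Day-21 blood | None at its planned time |
| Pre-surgery blood | None at its planned time |
| Blood one week after surgery and at 6 months | Arguably kept, through the flow-chart follow-up column |
| Second EBUS | None |
| Pre-surgery CT | None at its planned time |
| Resection specimen | No research provision, even if lobectomy goes ahead |

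Four of five blood samples are outstanding and two of them are unsecured. For removal between day 21 and surgery, three are outstanding and one is unsecured. The 7.1.3 visit may add one off-schedule blood sample and one scan. A scan before day 21 would fall more than 42 − 21 = 21 days before the earliest CT window opens.

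**3. How many patients.** The nearest figure in the protocol is 9.5% drug-related grade 3–4 events with pembrolizumab in 495 patients (4.1.7). That is not a removal rate: in Table 3 several grade 3 events only hold the drug. Assume removal of 1% to 5% in the combination arm.
- Expected number: 10 × 0.01 = 0.1 to 10 × 0.05 = 0.5.
- Chance of at least one: 1 − 0.99^10 = 0.10 to 1 − 0.95^10 = 0.40.

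**4. Effect of one such patient.** Suppose the removed patient differs by 1 to 2 SD (assumed) from the mean of the other nine.
- Arm mean without that patient: it moves by 1/10 = 0.1 to 2/10 = 0.2 SD. The shift is the same if a substitute takes the place and differs from the removed patient by that amount.
- Difference detectable with 80% power, two-sample t-test, 10 per arm, two-sided 0.05: 1.325 SD. The shift is 0.1/1.325 = 8% to 0.2/1.325 = 15% of this.
- Expected shift over the assumed range: 0.1 × 0.1 = 0.01 SD to 0.5 × 0.2 = 0.10 SD.

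**5. Loss of numbers alone.** By the normal approximation, power for a 1.25 SD difference falls from 0.80 with 10 per arm to 0.76 with 9 per arm. Selection is the larger issue.

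**The case against.** The strongest reply is that 5.10 was probably meant at treatment level. Its closing text speaks of follow-up after the end of treatment, 5.7.2 allows glucocorticoids for events of suspected immune cause, and Table 3 lets the drug be held and restarted. These suggest that patients with managed toxicity were expected to stay. That intent is plausible, but the operative sentence is mandatory and names the trial. The reply therefore supports clarifying the text and does not remove the conflict.

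Three stronger readings are tempting and are not supported:
- **That nothing is collected after removal.** The provisions listed above cover post-surgery blood at least arguably, a discontinuation visit, adverse events and disease status.
- **That 5.11 automatically substitutes a patient who tolerated treatment.** It applies only to patients who do not undergo the trimodality treatment. Lobectomy is standard of care for operable patients (4.1.6). A combination patient who has SBRT, one dose and then surgery has arguably received all three modalities and need not be replaced. Nothing says that a replaced patient's data are discarded.
- **That one substitution could overturn a result.** With 10 against 10 and no ties, one patient enters 10 of the 100 Mann-Whitney pairs. U could move from 23 (exact p = 0.043) to 33 (p = 0.22) only if all 10 pairings reversed from a start at the boundary. That is an outer bound, not an expected effect.

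Two further points stand. The number affected is small on any of these assumptions. The second EBUS is sedated and done only for research (10.3.9), so continuing it after serious toxicity burdens the patient.

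**Conclusion.** The point holds as a conflict in wording with a modest consequence. Section 5.10 acts at trial level on an undefined toxicity trigger and on illness that only prevents treatment, while 5.6.2, 5.6.2.1 and Table 5 act on the drug. For a patient removed before surgery, day-21 and pre-surgery blood (whichever are still due), the second EBUS if not yet done, the pre-surgery CT and research use of the specimen are not secured at their planned times. If that patient also never reaches surgery, 5.11 fills the place and leaves the analysis of the replaced patient open.

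At an assumed 1% to 5% removal, 0.1 to 0.5 of 10 combination patients are expected, with a 10% to 40% chance of at least one. The resulting bias in an arm mean is modest, and more frequent removal in the combination arm is a supposition.

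A reader might infer that the grade 3 or higher pneumonitis criterion in 8.1 is distorted too. The documents do not support this: adverse event recording continues, and nothing takes a replaced patient out of the count. Removal for an allergic reaction to the tracer (5.3.2.3) is a separate, minor matter.

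**What to change.** In 5.10, state that unacceptable toxicity and intercurrent illness end trial treatment only. Unless consent is withdrawn or the patient is lost to follow-up, continue:
- the scheduled blood samples and CT;
- the second EBUS, only if the patient is clinically fit and still agrees;
- research handling of the resection specimen, if the patient is operated on;
- adverse event recording.

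Analyse these patients in their randomised arm alongside any 5.11 replacement. Flag samples taken after early stopping or under corticosteroids, and repeat the comparisons without them.

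The cost is amendment wording; every assessment is already scheduled. The drawback is that a few samples will reflect partial dosing or steroid exposure. Under 5.8.1 the taper, where one is specified, lasts at least 4 weeks and starts only after improvement to grade 1 or less. For an event on day 20, steroids would end no earlier than 20 + 28 = day 48 and could extend to surgery. The repeat analysis may then resemble what the present rule would give. The gain is that the comparison of all randomised patients can be shown beside it.
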